1.0 Background & Rationale

Specialized Navy personnel are required to undertake duties while immersed in cold water for prolong periods. These dives regularly require the use of external thermal protection (i.e., wet suits and dry suits). However, external thermal protection during prolonged cold-water diving is often times insufficient to maintain body temperature and thermal comfort, thereby potentially negatively impacting the safety and success of diving missions. Accordingly, developing an alternative strategy that can improve tolerance to cold-water immersion is of important interest to Navy divers and special forces.

Mirabegron (Myrbetriq®, extended-release tablet, Astellas Pharma), is a medication approved by the Food and Drug Administration for the treatment of overactive bladder; the mechanism of action is stimulation of the beta-3-adrenergic receptor (1). However, mirabegron has additional effects that include the activation of beta-3-adrenergic receptors located on brown adipose tissue (1). Brown adipose tissue is considered to be highly thermogenic and contributes to non-shivering thermogenesis (i.e. the generation of heat in the absence of movement). Recent evidence indicates that resting energy expenditure (a direct reflection of thermogenesis) and supraclavicular skin temperature (an indicator of brown adipose tissue activation) are elevated for 3-4 hours after the acute administration of mirabegron in single doses ranging from 100 mg to 200 mg (2). However, it is not known which dose of mirabegron exerts the longest lasting thermogenic effects. Importantly, plasma concentrations of mirabegron peak 3-4 hours after administration (3, 4) and the biological half-life of mirabegron is 40-50 hours (4). Thus, the thermogenic effects of mirabegron might extend past 4 hours. This is important because many cold-water dives last longer than 4 hours.

2.0 Objective(s)

2.1 Primary Objectives

Specific Aim 1:

- a. Determine if acute mirabegron administration will increase thermogenesis during 6 hours of a mild cold stress challenge.
- b. Determine the dose of acute mirabegron administration that will produce the greatest increases in thermogenesis during 6 hours of a mild cold stress challenge.

Specific Aim 2:

- a. Determine if acute mirabegron administration will delay the fall in core temperature during a progressive cold-water immersion challenge.
- b. To determine if acute mirabegron administration will delay the onset of shivering during a progressive cold-water immersion challenge.

2.2 Secondary Objective

Specific Aim 1:

Determine if core temperature, mean skin temperature (6 thermocouples), heart rate (ECG), blood pressure (brachial artery auscultation), indices of shivering (e.g., oxygen consumption, surface mechanomyography (using 3 triaxial accelerometers) and the bedside shivering assessment scale), thermal perceptions (thermal comfort and thermal sensation), and brown adipose tissue activation using infrared thermography are influenced by the dose of mirabegron 6 hours of a mild cold stress challenge.

Specific Aim 2:

Determine if the shivering inflection point during the progressive cold-water immersion challenge is shifted following mirabegron ingestion.

2.3 Tertiary/Exploratory/Correlative Objectives**Specific Aim 3:**

To determine if variations in gut microbiome and their metabolites between participants explains the variability associated with different doses of acute mirabegron administration.

We will correlate measures of body composition derived from dual-energy X-ray absorptiometry (DEXA) to primary and secondary outcome measures.

3.0 Outcome Measures/Endpoints**3.1 Primary Outcome Measures****Specific Aim 1:**

Thermogenesis (i.e., resting energy expenditure) and thermogenesis area under the curve during the protocol. Thermogenesis will be measured using whole body indirect calorimetry, calculated using the Weir formula (5), will be measured every 30 minutes during the 6 hour protocols. Area under the curve for thermogenesis will be calculated to reflect the cumulative effect of mirabegron over time.

Specific Aim 2:

Core temperature deflection point during the progressive cold-water immersion challenge. Core temperature will be continuously measured using rectal thermistors. The point at which core temperature begins to fall (i.e., deflection point) will be identified using Prism 8 software by plotting core temperature vs. water temperature.

Specific Aim 3:

Gut microbiota phylotypes, fecal mirabegron concentration, and serum mirabegron concentration will be measured from samples obtained during the study (serum samples: pre-mirabegron/placebo and following 6 h of mild cold exposure; fecal samples: first bowel movement following 6 h of mild cold exposure). Samples will be assessed using bacterial DNA extraction and purification, polymerase chain reaction, and MinION analysis as well as metabolomics.

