Specific Aim 3: This aim will be addressed using the study design and visits used for Specific Aim 1 (a randomized, double-blind, placebo-controlled, cross-over experimental design). During these study visits, we will collect whole blood at pre-mirabegron/placebo and 15 minutes post the 6 h protocol. The whole blood will be allowed to clot and we will obtain serum samples for analyses. Participants will also be given fecal sample collection kits that they will take home to be used to collect fecal samples from their first bowel movement following each study visit. The serum and fecal samples will be sent to a colleague at Rutgers University for analyses. All samples will be de-identified prior to being sent to Rutgers University.

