- Surface Mechanomyography: Three triaxial accelerometers adhered to the skin using adhesive tape on the chest, upper back, and thigh will be used to assess shivering.
- Resting Energy Expenditure (thermogenesis): Expired oxygen, carbon dioxide, and ventilation will be collected from the whole-body calorimetry and used to calculate thermogenesis using the abbreviated Weir formula (5).
- International Physical Activity Questionnaire: Participants will complete this form to self-report and quantify their level of physical activity.
- Health history and demographics questionnaire: Participants will complete a health history questionnaire to ensure they meet the inclusion and exclusion criteria.
- Health history update questionnaire: Upon each visit to the laboratory participants will complete the health history update questionnaire to ensure no changes in their health history has occurred.
- Infrared Thermography Images: An infrared thermography camera will be used to measure skin temperature in the supraclavicular (i.e., collar bone) region. This provides a non-invasive estimate of brown adipose tissue activation (6).
- PAR-Q+: Participants will complete this questionnaire to ensure they meet the inclusion and exclusion criteria.
- 3-Day Dietary Log: Myfitnesspal.com (Under Armour) is a dietary log that will be used to quantify the type and amount of food and fluid that participants consume 3 days prior to each study visit.
- Body Composition: Participants will have their body composition measured using DEXA.
- Whole Blood Collection: 15 mL of whole blood will be obtained from an antecubital vein at pre-mirabegron/placebo and at 15 minutes post protocol using standard aseptic techniques defined by the World Health Organization.
- Fecal Sample Collection: Participants will be given fecal collection kits (DNA Genotek) and will be given verbal instructions from the collection kit directions on how to obtain samples as well as the pamphlet that contains these directions the after the study visits of Specific Aim 1. Participants will be instructed to obtain samples from their first bowel movement after each study visit.

Timeline of Procedures

Specific Aim 1

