8.0 Study Calendar

Specific Aims 1 and 3

	Screening	Study Visits 1-4				
	Day 1	Day 2	Day 3	Day 4	Day 5	
STUDY PROCEDURES						
Height	X					
Weight	X	X	X	X	X	

Urine pregnancy		X	X	X	X
Heart rate (electrocardiogram)		X	X	X	X
Arm Blood Pressure	X	X	X	X	X
Core temperature		X	X	X	X
Skin temperature		X	X	X	X
Perceptual scales		X	X	X	X
Bedside shivering scale		X	X	X	X
Surface mechanomyography		X	X	X	X
Resting energy expenditure		X	X	X	X
International Physical Activity Questionnaire (IPAQ)	X				
Health History Questionnaire	X				
Health History Update Questionnaire		X	X	X	X
Infrared Thermography Images		X	X	X	X
PAR-Q+	X				
3-Day Dietary Log		X	X	X	X
Body Composition	X				
Whole Blood		X	X	X	X
Fecal Samples		X	X	X	X

Specific Aim 2

	Screening	Study Visits 1-2	
	Day 1	Day 2	Day 3
STUDY PROCEDURES			
Height	X		
Weight	X	X	X
Urine pregnancy		X	X
Urine Specific Gravity		X	X
Heart rate		X	X
Arm Blood Pressure	X	X	X
Arterial oxygen saturation		X	X
Partial pressure of end tidal CO ₂		X	X
Ventilation		X	X
Core temperature		X	X
Skin temperature		X	X
Perceptual scales		X	X
Bedside shivering scale		X	X
Surface mechanomyography		X	X
International Physical Activity Questionnaire (IPAQ)	X		
Health History Questionnaire	X		
Health History Update Questionnaire		X	X
Infrared Thermography Images		X	X
PAR-Q+	X		
3-Day Dietary Log		X	X
Body Composition	X		

Specific Aim 3

See table for Specific Aims 1 and 3 above.

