Power Analysis: This aim is being conducted as an exploratory aim in conjunction with Specific Aim 1. As such, to be consistent, we expect to observe an effect size (δ) of 0.90 for the comparison of the gut microbiota in the placebo condition versus 200 mg of mirabegron. Given this effect size, 10 participants will be needed to achieve a power of 0.99 with an alpha level set at 0.05. To account for possible attrition, we plan on recruiting up to 30 participants.

Statistical Approach:

Principal Coordinate Analysis will be performed with group samples and any outliers will be identified. T-tests, and/or ANOVA will be performed to identify significant differences. Statistical analysis to detect variation between samples will be carried out using student t-test or Mann-Whitney test depending on data distribution. Multivariate statistics will be incorporated in a web-based tool Metastats, which can reveal, with high confidence, discriminatory functions between the replicated metagenome dataset of the gut microbiota of humans. In addition, the ShotgunFunctionalizeR and/or Primer E packages will be used for this analysis.

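### Aim 3 uses the microbiome to explain response to mirabegron, but all stool follows that visit's ingestion and the plan names no drug-free sample as predictor, no linking analysis and no collection time

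*Combined protocol and SAP*

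**What the plan says.** Section 2.3 gives the microbiome an explanatory role: the aim is to learn whether "variations in gut microbiome and their metabolites between participants explains the variability associated with different doses of acute mirabegron administration". I take the response in question to be thermogenesis, the primary outcome of Aim 1.

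The sampling rule is the same wherever it appears:

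- Section 3.1, Specific Aim 3: "fecal samples: first bowel movement following 6 h of mild cold exposure". In the same sentence serum does get a pre-dose sample: "serum samples: pre-mirabegron/placebo and following 6 h of mild cold exposure".
- Section 5.0, Specific Aim 3: participants take kits home to "collect fecal samples from their first bowel movement following each study visit".
- Section 7.0, Fecal Sample Collection: "Participants will be instructed to obtain samples from their first bowel movement after each study visit".
- Section 8.0: the row "Fecal Samples" is marked for the four study visits and is blank at screening.

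Section 12.0, Specific Aim 3, then uses the microbiota as an outcome. Its power statement takes an effect size of 0.90 "for the comparison of the gut microbiota in the placebo condition versus 200 mg of mirabegron". The planned methods are an ordination, t-tests or ANOVA, Mann-Whitney tests and software packages for comparing samples.

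Section 5.0 randomises the order of placebo and three doses over four visits. Section 7.0 separates visits by at least 10 days.

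**The concern.** The same measurement has two roles: it is meant to explain the response to the drug, and it is also tested as something the drug may change. Stool from a mirabegron visit cannot serve both roles without a rule. If the drug shifts the microbiota more in people who absorb more or respond more, that stool will correlate with that visit's thermogenesis even when the participant's usual microbiome has no influence. The stated question is about the usual microbiome.

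Two gaps make this worse. No listed method relates microbiome to thermogenesis, so the plan followed as written compares samples with each other and leaves the objective unaddressed. And with four stools per participant and no designated predictor, the choice of sample could be made after results are seen.

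Timing is a related matter. The first bowel movement after the visit has no upper time limit, collection is at home, and samples may be posted directly to the analysing laboratory. Fecal mirabegron concentration stands under section 3.1. If time since ingestion is not recorded at collection, it cannot reliably be recovered later.

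**Working it through.** **The plan's own figure.** Section 12.0, Aim 3: 10 participants, effect size 0.90, alpha 0.05, power 0.99. Read as a paired standardised difference, the noncentrality is 0.90 × √10 = 2.85 on 9 degrees of freedom. Power is then 0.72 two-sided or 0.84 one-sided, not 0.99. About 0.98 two-sided is reached only on an unstated assumption, such as 0.90 on the per-condition SD with a within-person correlation of 0.8. That is a separate issue, and nothing below depends on it.

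**Which samples exist.** There are four stools per completer: three after mirabegron and one after placebo. Section 17.1 agrees: $100 in total at $25 per sample is 100 / 25 = 4 samples, which leaves no baseline.

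**How drug-free the placebo-visit stool is.**
- If placebo is equally likely in each of four positions, it comes first in 1/4 of participants: 2.5 of 10, or 7.5 of 30. In the other 3/4 it follows at least one mirabegron dose.
- A 10-day gap is 240 h. At the 50 h half-life of section 7.0 this is 240 / 50 = 4.8 half-lives, leaving 0.5^4.8 = 3.6% of drug. At the 40 h lower end in section 1.0 it is 6 half-lives, leaving 1.6%.
- These are drug half-lives. The documents give no recovery time for the microbiota.

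**Why the sample chosen matters (illustration, assumed values).** Let the usual profile be M0 with SD 1 and no effect on response. Let individual drug exposure E (SD 1) correlate 0.7 with response Y. Let the mirabegron-visit profile be M1 = M0 + 0.9 + s·E. Then corr(M1, Y) = 0.7s / √(1 + s²).
- s = 0: 0. A shift that is the same in everyone creates no spurious correlation within a dose.
- s = 0.5: 0.35 / 1.118 = 0.31.
- s = 1: 0.7 / 1.414 = 0.49.

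The placebo-visit profile, if recovered to M0, correlates 0 with Y throughout. The problem therefore needs a drug effect on the microbiota that varies between people along with response. The plan neither assumes this nor rules it out.

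**Collection time.** From section 7.0: 0.5 h from ingestion to chamber entry + 6 h in the chamber + 0.25 h to the final blood draw = 6.75 h as the earliest point. No latest point is given.

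**Precision of a predictor analysis.** The smallest correlation detectable with 80% power at two-sided 0.05 is, by Fisher z, tanh[(1.96 + 0.84) / √(n − 3)]. With n = 10: tanh(2.80 / √7) = 0.79. With n = 30: tanh(2.80 / √27) = 0.49.

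**The case against.** The strongest reply is that the planned samples already contain what is needed. Every completer gives a stool with no active drug at that visit, at least 10 days after any earlier dose. A reader might infer from the post-dose sampling that cause and effect can never be separated, or that Aim 3 cannot be answered from these samples. The documents do not support that: the placebo-visit stool can be the predictor, and what is missing is the sentence that says so and an analysis that uses it.

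A reader might also take the 0.90 as the sponsor's prediction that mirabegron alters the microbiota. Section 12.0 introduces it for consistency with Aim 1, uses the same value for energy expenditure and rectal temperature, and cites no microbiota data. It is a carried-over planning figure. It does show that the microbiota is treated as an outcome, but not how large any effect would be.

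Three further points stand. Fecal drug concentration can only be measured after dosing, so post-dose collection has a purpose. The kit instructions are not in the documents and may already ask for a date and time, so it is only safe to say that the protocol does not require them. Nothing in the documents supports a figure for how much collection times will vary. Finally, Aim 3 is called exploratory, although its measures are listed under primary outcomes.

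None of this removes the gap in specification.

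**Conclusion.** The point holds as a gap between objective, sampling and analysis. No stool is planned before ingestion, the one sample per completer with no active drug at that visit is not named as predictor, and no analysis links microbiome to thermogenesis. An association based on mirabegron-visit stool would have no clear direction. Separately, the documents require no collection time for an outcome that depends on time since dose.

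The gap can be closed with the planned samples, so it is a low-cost improvement to an exploratory aim and not a failed design. The 1-in-4 figure assumes balanced order. The correlations of 0.31 and 0.49 in the illustration rest on assumed values and show only that the bias can be material. Even the corrected analysis fixes time order without proving cause, and with 10 to 30 participants it could detect only fairly strong associations (0.79 to 0.49), before any allowance for testing many taxa.

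**What to change.** **Sections 3.1 and 12.0.** Prespecify the placebo-visit microbiome profile as the explanatory variable for each participant's mirabegron-minus-placebo thermogenesis at the three doses. Name the summary of the profile and the model. One option is to regress the difference in thermogenesis area under the curve on dose and a leading principal coordinate, with a random participant effect. Add a sensitivity analysis by visit order or prior mirabegron exposure. State that mirabegron-visit stool is outcome data only.

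**Section 7.0.** Have participants record the date and time of collection on the kit. Use hours since ingestion as a covariate for fecal mirabegron concentration. In the placebo-versus-200 mg microbiota comparison use it only in a sensitivity analysis, because it arises after randomisation and could itself be affected by treatment.

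**Cost.** Text in three sections, a short model specification and one line on the kit, with no new visit or sample. The predictor would rest on one sample per participant, be lost if the placebo visit is missed, follow the same 6 h cold exposure as the others, and in about 3 of 4 participants follow an earlier dose with no stated microbiota recovery time. A kit handed out at screening for use before Study Visit 1 would be better, at the price of one extra sample each; it is optional.

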3.2 Secondary Outcome Measures**Specific Aim 1:**

Core temperature, mean skin temperature (6 thermocouples), heart rate (ECG), blood pressure (brachial artery auscultation), indices of shivering (e.g., oxygen consumption, surface mechanomyography (using 3 triaxial accelerometers) and the bedside shivering assessment scale), thermal perceptions (thermal comfort and thermal sensation), and brown adipose tissue activation using infrared thermography

Specific Aim 2:

The shivering inflection point during the progressive cold-water immersion challenge. Shivering will be assessed via oxygen consumption, surface mechanomyography (using 3 triaxial accelerometers), and the bedside shivering assessment scale. The core temperature immediately prior to the onset of shivering during the progressive cold-water challenge will be identified using Prism 8 software by plotting shivering vs. core temperature.

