empty water immersion tank. Then they will be instrumented for the measurement of heart rate (3-lead ECG), blood pressure (brachial artery auscultation), core temperature (rectal thermistor), and indices of shivering (surface mechanomyography using triaxial accelerometers at 3 anatomic sites (chest, upper back, and thigh), oxygen consumption via ventilation and expired gases, and the bedside shivering assessment scale). Thermal perceptions will be assessed using Likert scales for thermal discomfort and thermal sensation. Following 10 minutes of resting baseline measurements, infrared thermography will then be used to measure skin temperature of the supraclavicular fossa as an estimate of brown adipose tissue activation and thermal perceptions will be assessed. The participants will then ingest either mirabegron (100 mg) or a placebo tablet. The dose of mirabegron will be determined from the results of Specific Aim 1. The dose of mirabegron that elicits the greatest increase in thermogenesis in Specific Aim 1 will be used in Specific Aim 2. The measurement of supraclavicular fossa skin temperature (infrared thermography) and thermal perceptions will be assessed every 10 minutes prior to the progressive cold-water challenge. After 30 minutes of seated rest, pre-immersion measurements of heart rate, blood pressure, core temperature, shivering, and thermal perceptions will be conducted and an infrared thermography image will be taken. Then, the water immersion tank will be filled up to the participant's neck with 35°C (95°F) water. Heart rate, blood pressure, core temperature, and shivering indices will be continuously measured. Infrared thermography and thermal perceptions will be obtained every 5 minutes throughout the progressive cold-water challenge. The water will be cooled at a rate of 12°C per hour until the water temperature reaches 10°C (50°F), the participant can no longer tolerate the cold water, or core temperature reaches 35.5°C (95.9°F). This is 0.5°C higher than the clinical definition of hypothermia. Also, the risks associated with hypothermia are core body temperature-dependent and not dependent on time (7). Upon completion of the progressive cold water challenge, the water in the tank will be rapidly emptied. Participants will gently towel dry and will be able to don a circulating warm water perfused suit and/or use a mylar blanket to reestablish core temperature. If participants complete the informed consent/screening visit and all study visits, we expect that they will spend a total of ~11 hours in the study.

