12.0 Statistical Considerations

Specific Aim 1

Power Analysis: Using data from Loh et al. (2) we expect to observe an effect size (δ) of 0.90 for the comparison of resting energy expenditure in the placebo condition versus 200 mg of mirabegron. Given this effect size, 10 participants will be needed to achieve a power of 0.99 with an alpha level set at 0.05. To account for possible attrition, we plan on recruiting up to 30 participants.

Statistical Approach: We will compare the primary (i.e., thermogenesis) and secondary (i.e., core temperature, skin temperature, heart rate, blood pressure, indices of shivering, thermal perceptions, and infrared thermography images) dependent variables using mixed effects ANOVA (i.e., mirabegron dose x time) followed by Tukey's post hoc procedure if a significant interaction or main effect is found from the ANOVA analyses. We will also calculate the thermogenesis area under the curve for each dose of mirabegron. These values will be compared using repeated measures ANOVA followed by Tukey's post hoc procedure if a significant main effect is found from the ANOVA analysis. We will also perform correlation analyses to determine the relation between body composition and our primary and secondary dependent variables. The alpha level will be set at $P < 0.05$ for all analyses.

Specific Aim 2

Power Analysis: Similar to Specific Aim 1 and the data from Loh et al. (2), we expect to observe an effect size (δ) of 0.90 for the comparison of rectal temperature in the placebo condition versus the mirabegron condition. Given this effect size, 10 participants will be needed to achieve a power of 0.99 with an alpha level set at 0.05. To account for possible attrition, we plan on recruiting up to 30 participants.

Statistical Approach: The primary (i.e., core temperature deflection point) and secondary (i.e., onset of shivering inflection point) dependent variables from the mirabegron and placebo trials will be compared using paired t-tests to determine if mirabegron improves cold-water immersion tolerance. Mixed effects ANOVA will be used to compare the remaining dependent variables between conditions (i.e., mirabegron vs. placebo) and across time. If a significant

interaction or main effect results from the ANOVA analyses, we will use the Holm-Sidak post hoc test to determine where differences exist. The alpha level will be set at $P < 0.05$ for all analyses.

Specific Aim 3

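### Primary objective 2b asks whether shivering starts later, but the only onset outcome is core temperature at onset, which need not change when it does

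*Combined protocol and SAP*

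**What the plan says.** All references are to the combined protocol and SAP, Specific Aim 2.

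- **Section 2.1, primary objective 2b:** "To determine if acute mirabegron administration will delay the onset of shivering during a progressive cold-water immersion challenge".
- **Section 2.2, secondary objective:** "Determine if the shivering inflection point during the progressive cold-water immersion challenge is shifted following mirabegron ingestion".
- **Section 3.1, primary outcome:** the core temperature deflection point only, which "will be identified using Prism 8 software by plotting core temperature vs. water temperature". No shivering variable is listed.
- **Section 3.2, secondary outcome:** the shivering inflection point, with one stated derivation: "The core temperature immediately prior to the onset of shivering during the progressive cold-water challenge will be identified using Prism 8 software", from a plot of shivering against core temperature.
- **Section 12.0:** shivering onset is again secondary: "secondary (i.e., onset of shivering inflection point) dependent variables from the mirabegron and placebo trials will be compared using paired t-tests". For everything else, "Mixed effects ANOVA will be used to compare the remaining dependent variables between conditions (i.e., mirabegron vs. placebo) and across time".
- **Section 7.0:** "Heart rate, blood pressure, core temperature, and shivering indices will be continuously measured". The water cools from 35°C at 12°C per hour. Immersion ends at 10°C water, at the participant's limit of tolerance, or at the core temperature limit.

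No section defines the time or the water temperature at which shivering starts.

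**The concern.** A delay is a statement about when shivering starts. Core temperature just before onset is a statement about how cold the body is when it starts. The second fits the section 2.2 objective, but it answers 2b only if the drug works by moving the threshold.

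Objective 2a proposes that mirabegron delays the fall in core temperature. If it does that and nothing else, each participant reaches the same threshold later. Shivering is then delayed, yet core temperature at onset is the same at both visits. The trial could correctly report a later fall in core temperature and also report no effect on shivering onset when onset was in fact later. A larger sample would not help.

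The rank is also inconsistent. Shivering onset is a primary objective in section 2.1, but its only outcome is secondary in sections 3.2 and 12.0.

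**Working it through.** **The plan's own figure.** Section 12.0 gives one Aim 2 power figure: 0.99 with 10 participants at effect size 0.90, for rectal temperature. Read as a standardised paired difference in a two-sided paired t-test, those inputs give 0.72. That is a separate matter. No effect size is stated for shivering onset, so there is no figure to reproduce here.

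**Axes compared.** The deflection point is read against water temperature, which tracks time on the ramp: 12/60 = 0.2°C per minute, or 5 minutes per °C, and (35 − 10)/0.2 = 125 minutes in all. Shivering onset is read against core temperature, which does not track time in this way.

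**Illustration (assumed values, not from the documents).** Baseline core temperature 37.2°C; shivering threshold 36.8°C at both visits; fall of 0.02°C/min after deflection; deflection at 22°C water on placebo and 19°C on mirabegron; within-visit SD 8 min for deflection time and 0.08°C for threshold.

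1. Deflection time: (35 − 22)/0.2 = 65 min and (35 − 19)/0.2 = 80 min.
2. Deflection to threshold: (37.2 − 36.8)/0.02 = 20 min.
3. Shivering onset: 85 and 100 min, in water at 35 − 0.2 × 85 = 18°C and 35 − 0.2 × 100 = 15°C. The delay is 15 min.
4. Core temperature at onset: 36.8°C both times, difference 0.
5. Paired SDs: deflection 8√2 = 11.3 min; core temperature at onset 0.08√2 = 0.113°C; onset time √[2(8² + (0.08/0.02)²)] = √160 = 12.65 min.

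Power is for a two-sided paired t-test at alpha 0.05 (noncentral t with noncentrality √n × mean difference / paired SD). Cells show n = 10, then n = 30.

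| Outcome | Later deflection, 15-min delay | Same deflection, slower fall, 15-min delay | Threshold 0.1°C lower, 5-min delay |
|---|---|---|---|
| Core temperature at onset (planned) | 5%, 5% | 5%, 5% | 70%, >99% |
| Deflection point (planned) | 96%, >99% | 5%, 5% | not affected |
| Onset time (not planned) | 91%, >99% | 86%, >99% | 20%, 55% |

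The slower-fall column assumes deflection at 65 min at both visits and a fall of 0.4/35 = 0.0114°C/min on mirabegron. Its paired SD for onset time is √(8² + 4² + 8² + 7²) = 13.9 min. The third column's delay is 0.1/0.02 = 5 min. The 5% entries are the false-positive rate and follow directly from what was assumed.

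**Sensitivity of the onset-time figure.** With paired SD from 10 to 20 min, power for 15 min runs from 99% to 56% at n = 10 and is about 98% or more at n = 30.

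Section 9.0 cites falls slower than the assumed 0.02°C/min. These are averages under other protocols, so they are only a guide.

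- *Under 1°C in 60 min at 15°C:* at 1/60 = 0.0167°C/min, power at n = 10 is 89%.
- *37.6 to 37.0°C over 88 min in ice:* 0.6/88 = 0.0068°C/min, so the threshold is reached 0.4/0.0068 ≈ 58.7 min after deflection. Onset would fall at about 124 and 139 min, against a ramp of 125 min. With within-visit SD √(8² + 11.7²) ≈ 14.2 min, about 46% of placebo visits and 83% of mirabegron visits would reach the end of the ramp before shivering. The power figures above do not then apply.

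**The case against.** **Delay need not mean clock time.** Objective 2a also speaks of delay, and its outcome is a point on a water-temperature plot. A shift of shivering to a lower core temperature is a defensible reading of 2b, and objectives 2b and 2.2 may be one objective listed twice. This stands as far as it goes. But then one objective carries two ranks, and there is still no outcome for when shivering starts.

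**The expected difference of zero is an assumption.** It needs a threshold that depends on core temperature alone and is unchanged by the drug. In the illustration, onset occurs in water 3°C colder on mirabegron, and the documents do not say that this leaves the threshold alone. This stands in full.

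**Other analyses cover part of it.** Shivering indices are recorded continuously, and the condition-by-time ANOVA, if they count among the remaining variables, may show less shivering at given times. That is a real mitigation, but it defines no onset and estimates no delay.

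**Onset time has its own weakness.** With slow cooling, many visits could end without shivering. This also stands, so the censoring rule has to be part of the outcome definition. The planned outcome is undefined at the same visits, and section 12.0 gives no rule for them.

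A reader might infer that Aim 2 as a whole will miss a real effect. The documents do not support that: in the main illustration the deflection point would be positive.

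**Conclusion.** The mismatch between objective and outcome is certain from the text, as is the inconsistent rank of 2b. The consequence is conditional: if cooling is delayed and the threshold is unchanged, the planned test has an expected difference of zero although shivering starts later. If the threshold shifts, the planned outcome works and is the more sensitive measure (70% against 20% at n = 10 for 0.1°C, on the assumed values).

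Two stronger readings should be resisted. One is that the trial will report a false negative on shivering; the documents give no basis for saying how likely an unchanged threshold is. The other is that 91% against 5% measures the power lost; those figures rest on assumed cooling rates and SDs, and the 5% is built into the scenario.

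No data are lost and the primary deflection-point result stands. What is at risk is the answer to 2b. It should be fixed before analysis, because choosing an index and an onset rule afterwards, from three available shivering measures, would be post hoc.

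**What to change.** 1. **Add an outcome for 2b.** Use measured water temperature at shivering onset, the axis already used for the deflection point, with elapsed immersion time as the alternative scale. The two are only approximately interchangeable, because section 5.0 gives the cooling rate as approximate. Name one shivering index and state the onset rule. Keep core temperature at onset for the section 2.2 objective.
2. **Give 2b one rank in sections 2, 3 and 12.** Either label it secondary, as sections 3.2 and 12.0 already treat it, or list it in section 3.1 with a test order or alpha split against the deflection point.
3. **Define censoring within the outcome.** Treat a visit that ends without shivering as censored at the end of immersion, and record the reason. Prespecify one paired method that handles censoring and gives an effect estimate with a 95% CI. The choice of method is open, but a rank test alone would not supply the estimate.

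**Cost.** Wording changes and one derived variable, since the recordings are already planned. If 2b stays primary, alpha must be shared: on the assumed values, testing onset time at 0.025 lowers power from 91% to 83% at n = 10 and leaves it above 99% at n = 30. Onset time and water temperature at onset are less sensitive than core temperature at onset to a pure threshold shift, which is why both kinds of measure are kept.
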